STUDY: Perioperative Ketamine in Opioid-Tolerant Patients Undergoing Lumbar Spine Surgery: A

Randomized, Double-blind, Place-controlled Trial

Principal Investigator: [name], PhD, MBA

IRB: STUDY19020144

NCT: 04220489

Study Protocol – Approved 09/03/2019

Basic Information

1. * Title of study:

Perioperative Ketamine in Opioid-Tolerant Patients Undergoing Lumbar Spine Surgery: A Randomized, double-blind, placebo-controlled trial

2. * Short title:

Perioperative Ketamine in Opioid-Tolerant Patients Undergoing Lumbar Spine Surgery

3. * Brief description:

The goal of this study is to determine whether comprehensive perioperative administration of the NMDA receptor antagonist ketamine can increase postoperative pain tolerance and reduce opiate consumption in chronic back pain patients undergoing spinal laminectomy/fusion when compared to placebo

Design: Prospective, Randomized, Double-Blind, Placebo Controlled trial involving opiate-dependent patients undergoing lumbar spine surgery. Opioid dependence will be defined as greater than 60 mg oral morphine equivalents/day for greater than one week. Intraoperatively, patients will receive a 1 mg/kg dose of intravenous ketamine or saline with 15 minutes after induction of general anesthesia. Thereafter, a continuous infusion of 0.20 mg/kg/hr ketamine with a maximum dose of 20 mg/hr or saline will be run to conclude at 48 hours after the end of the surgery (fascial closure). The primary outcome measure will be hydromorphone PCA usage during the first 72 hours postoperatively. Secondary outcome measures will be VAS pain scores at rest and with movement in PACU, 24 hr, 48 hr, 72 hr, 2 week (post-op visit), 6 week follow-up visit, as well as, McGill Pain Questionnaire, Pain Catastrophizing Scale, and emotional distress surveys assessing depression and anxiety at preop/screening, postop and 6 week follow-up (PROMIS Emotional Distress-Anxiety Short Form, PROMIS Emotional Distress-Depression Short Form), as well as a Neuro-QOL Short Form v1.1 - Satisfaction with Social Roles and Activities.

4.	* Principal investigator:
	[name]

5 .	*	Does	the	investigator	have a	financial	interest	related	to this	researd	:h?
	- 0	Ye	s 💿	No							

6. * Will an external IRB act as the IRB of record for this study?

O Yes No

- 7. * What kind of study is this? Single-site study
- 8. Attach the protocol:
 - Sponsor/Multicenter protocol
 - Investigator-initiated protocol
 - Emergency Use Consent/ Protocol/ FDA Form 3926

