The goal of this study is to determine whether comprehensive perioperative administration of the NMDA receptor antagonist ketamine can reduce postoperative pain tolerance and opiate consumption in chronic back pain patients undergoing spinal laminectomy/fusion when compared to saline placebo.

Investigators hypothesize that administration of a ketamine infusion intraoperatively and for 48 hours postoperatively will significantly reduce postoperative opiate consumption and VAS pain scores in chronic back pain patients undergoing spinal laminectomy/fusion when compared to those in the placebo arm.

2. * Describe the relevant prior experience and gaps in current knowledge including preliminary data. Provide for the scientific or scholarly background for, rationale for, and significance of the research based on existing literature and how it will add to existing knowledge: Patients with chronic pain are some of the most difficult to manage during the perioperative period, in part because they are often on large doses of opioids, rendering them relatively tolerant to the opioids used in the perioperative period. Several lines of evidence suggest that ketamine, administered intraoperatively, and/or post-operatively may be solution to this problem. Even more intriguingly, there is evidence to suggest that perioperative ketamine may have long term effects on opioid use. However, nearly all of the studies up to this point have investigated the short-term effects of ketamine on post-operative pain and opioid consumption. This pilot study will investigate the impact of intra-operative and post-operative ketamine on pain and opioid consumption six weeks after surgery and will support a larger NIH funded trial.

Central Sensitization and the NMDA receptor: evidence from preclinical models of pain

Seminal studies by Woolf and colleagues provided mechanistic insight into a phenomenon long appreciated by patients and clinicians alike: intense noxious stimulation results in an increase in pain from the site injury as well as from surrounding tissue well outside the injured tissue. The

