The analgesic and/or opioid sparing effects of ketamine has been studied in healthy subjects and pain patients including those suffering from glossopharyngeal neuralgia, postherpetic neuralgia, fibromyalgia muscle pain, stump and phantom limb pain, peripheral neuropathic pain, central neuropathic pain, chronic post-traumatic pain, pain due to arteriosclerosis obliterans (Fisher, 2000). The application of ketamine to the perioperative period as a "preemptive" or "preventive" analgesic has met with mixed results. Many of the earlier studies compared a preincisional with a postincisional dose of ketamine and saw no difference between the two. However a meta-analysis of 37 subsequent trials of the use of perioperative ketamine compared to placebo found that "ketamine in subanaesthetic dose is effective in reducing morphine requirements in the first 24 hours after surgery and also reduces postoperative nausea and vomiting" and "adverse effects are mild or absent." (Bell, 2006). Twenty-seven of 37 trials found that perioperative ketamine reduced rescue analgesic requirements or pain intensity, or both. Ten trials found no significant difference between ketamine and placebo, three of which were considered non-sensitive. Of

those that did find an effect, it was generally reported to give a 30-50% reduction of rescue analgesics. Another review that used VAS scores at 24 hours after surgery as the primary outcome, and included an overlapping subset of studies did not find an overall significant effect of ketamine (Subramaniam, 2001).

Dose Range and side effects

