This medical record review to identify eligible candidates is minimal risk and that the rights and welfare of subjects will not be adversely affected The primary surgeon will identify patients who are prescreened via medical record to be eligible for inclusion, ask them if they would be interested in participating, and if so, the enrollment and consent process would be initiated. Participating neurosurgeons include Drs. [name], who will identify eligible patients. Informed consent will be performed by this Neurosurgeon, the PI, or other co-investigator in the study. Enrollment will be performed by the study coordinator and/or trained representative from the Acute Interventional Perioperative Pain Service (AIPPS). Enrollment will include review of eligibility, and detailed explanation of the study.

5. * Describe all compensation/incentives offered to participants and timing of these offers:

Participants will be compensated up to \$100 for travel and parking expenses related to Pre-Op Visit (\$50) and 6-Week Follow-up visit (\$50)

Recruitment materials: (attach all material to be seen or heard by subjects, including advertisements and scripts)

Document Category Date Modified Document History

There are no items to display

View: Pitt SF: Study Design

Study Design

1. Total number of subjects to be enrolled at this site (enter -1 for chart reviews, banking, registries):
20

2. Describe and explain the study design:

This study is being proposed as a pilot study to inform the feasibility and direction of a larger P01 NIH funded trial.

3. Describe the primary and secondary study endpoints:

Primary Outcome measure:

- ¬ Pre- and post-surgical pain rating
- \neg Pre- and post-surgical opioid utilization (in morphine equivalent units in the PACU and post-operative period until discharge, at 14 days, and at 6 weeks follow-up)
- ¬ Pre- and post-surgical opioid analgesic efficacy

Secondary outcome measures:

- ¬ Mcgill Pain Questionnaire-Short Form
- ¬ Pain Catastrophizing Scale
- ¬ PROMIS Emotional Distress-Anxiety Short Form
- ¬ PROMIS Emotional Distress-Depression Short Form
- ¬ Neuro-QoL Short Form v1.1 Satisfaction with Social Roles and Activities
- ¬ Cold Pressor Test

4. Provide a description of the following study timelines:

Duration of an individual subject's active participation:

6 weeks

Duration anticipated to enroll all subjects:

5 months

Estimated date for the investigator to complete this study (complete primary analyses):

10/31/2019

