5. List the inclusion criteria:

Patients undergoing lumbar spine surgery of at least one level, and no more than 4 levels.

Patients with chronic back pain (>3 months)

ASA 1-3

Age 18-65

Opiate-dependent, meeting both of the following criteria:

- 1.Daily opiate use for at least 2 months
- 2. Oral morphine equivalent of 60 mg/day or higher

- 6. List the exclusion criteria:
 - -Intolerance or known allergy to ketamine
 - -History of increased intraocular pressure (> 22mmHg)
 - -Uncontrolled hypertension (systolic blood pressure greater than or equal to 180, diastolic blood pressure greater than equal to 100)
 - -Increased intracranial pressure (signs including:Behavior changes, Decreased consciousness, Headache, Letharqy
 - -Neurological symptoms, including weakness, numbness, eye movement problems, and double vision, seizures, vomiting)
 History of psychosis

Pregnancy

Patients with significant liver disease (signs and symptoms of liver injury, such as discolored skin and eyes that appear yellowish, abdominal pain and swelling, Itchy skin that doesn't seem to go away, Dark urine color, Pale stool color, Bloody or tar-colored stool, Chronic fatigue, Nausea, Loss of appetite, with or without elevated LFTs: AST > 120 IU/ml, AP >130 IU/ml, and ALT >40 IU/ml)

- -Patients with exposure to CYP3A and / or CYP2B6 inhibitors, including the herbs and the over-the-counter compounds (list of drugs can be found at http://www.fda.gov/drugs/developmentapprovalprocess/developmentresources/druginteractionslabeling/ucm093664.htm)
- 7. Will children or any gender, racial or ethnic subgroups be explicitly excluded from participation?
 - Yes No
 - * Identify the subgroups and provide a justification: Presbyterian Hospital is an adult-only facility
- 8. Describe the power analysis used and cite your method of statistical analysis. If a power analysis is not possible, thoroughly justify the sample size required for the study, including appropriate literature citation (alternatively provide page reference in attached protocol):

 This is a pilot to support a P01 program pilot application to the NIH, so the data will be analyzed mainly using descriptive statistics. Additional statistical analysis methods such as a 2-sample t test to compare significance between groups may also occur.

View: Pitt SF: Research Activities

Research Activities

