Randomization will occur by a computer based system at a 1:1 ratio. The Investigational Drug Pharmacy will create the randomization log and IDS will randomize the subject independent of the research team. The study drug/placebo will look identical to maintain the blind for all clinicians and research staff involved.

At the day of surgery, subjects will be seen by team members of the Acute Interventional Perioperative Pain Service preoperatively. Pregnancy will be assessed via medical record, as it is standard of care for these patients to take a pregnancy test day of surgery. Since the ketamine infusion will occur for 48 hours while patient is in the hospital, there is little risk of becoming pregnant during study drug treatment period

Enrolled participants will receive a 1 mg/kg dose of intravenous ketamine or saline 15 minutes after induction of general anesthesia. Thereafter, a continuous infusion of 0.20 mg/kg/hr ketamine or saline with a maximum dose of 20 mg/hr will be run to conclude at 48 hours after the end of the surgery (fascial closure).

A standardized general anesthesia protocol will be used by the hands-on provider. All drugs used intraoperatively, including total hydromorphone dose, will be collected from the electronic medical record.

The amount of narcotics and non-narcotic analgesics administered in the operative and postoperative period will be collected from the electronic chart from day of surgery until discharge. VAS pain scores will be collected

from the PACU until discharge from the hospital.

Pain will be monitored every four hours, except during the night when the participant is asleep. We will use a scale from 0-10, 0 being no pain, 5 being moderate pain and 10 being the worst imaginable pain. The participant will also be asked to score pain at its best and worst over the period since they were last asked.

Post-Op Visit: Approximately 1 hour

Patients will follow-up at Neurosurgery clinic at 10-14 days postoperatively. At this time daily opioid usage will be assessed and converted to morphine equivalents/24 hr. At this visit, the McGill Pain questionnaire-Short form, pain medication review form, and the Pain Catastrophizing Scale (PCS) (Sullivan, 1995). PROMIS Emotional Distress-Anxiety Short Form and PROMIS Emotional Distress-Depression Short Form, Brief Psychiatric Rating Scale and Neuro-QoL Short Form v1.1 - Satisfaction with Social Roles and Activities will also be completed by the participant.

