 - No subjects assigned to the placebo and experimental arms of the research study will continue to undergo a commonly used diagnostic/treatment approach
- 2. Describe the commonly used diagnostic/treatment approaches that will be withheld from subjects assigned to the placebo arm of this research study: No commonly-used treatment approach will be withheld from the subjects assigned to the placebo arm of this research study.
- 3. Is enrollment into this study limited to individuals in whom the commonly used diagnostic/treatment approaches are known to be ineffective or intolerable?
 - Enrollment into this study is limited to individuals who are opioid tolerant and therefore difficult to treat regarding post operative pain management. Subjects in both arms will receive the same standard of care treatment for post-operative pain management.
- 4. Provide a scientific justification for the placebo-control arm of this research study:

The placebo-control arm will allow for the clinicians to remain blinded to the treatment allocation of participants which will greatly improve the value of the pilot. This research is intended to develop an intervention (continuous, low dose ketamine infusion for 48 hours post-op) that can be implemented in the population from which trial participants are drawn (Opioid tolerant patients). Further, this trial does not require participants to forgo treatment they would otherwise receive

- 5. How long will subjects participate in the placebo arm? Justify why this duration is necessary:
 Subjects randomized in the placebo arm will receive the saline placebo in the exact same fashion as the intervention arm--intraoperatively and then for 48 hours post-operatively.
- 6. How frequently will the subject's condition or disease be monitored and compare that to the frequency of monitoring associated with standard care for this disease/condition?
 Participants in both groups will be monitored by the research team while in the hospital for incidence of adverse events, so they will be monitored more frequently than the standard of care.
- 7. What specific endpoints will result in discontinuing a subject's participation due to worsening of the subject's disease or condition? The same stopping criteria for the intervention arm will be applied to the placebo arm, because clinicians will be blinded to treatment allocation.

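### The 72-hour primary outcome counts one opioid by one route, so opioid given any other way is scored as a reduction; it needs reconciling with the all-opioid primary outcome listed elsewhere in the protocol

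*Protocol*

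**What the plan says.** The brief description in the Protocol (Basic Information, item 3) fixes a drug, a route and a window: "The primary outcome measure will be hydromorphone PCA usage during the first 72 hours postoperatively". It does not say how other opioids are converted, or what happens to the score when the PCA stops, the route changes or the patient goes home.

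Study Aims item 1 states the hypothesis more broadly: the ketamine infusion "will significantly reduce postoperative opiate consumption and VAS pain scores in chronic back pain patients".

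Study Design item 3 gives another list of primary outcomes. Its opioid entry is "opioid utilization (in morphine equivalent units in the PACU and post-operative period until discharge", with further assessments at 14 days and 6 weeks. It is not limited to one drug or route, and it has no 72-hour window.

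Research Activities item 1, which describes the visits in detail, schedules no PCA. Its only mention of hydromorphone is intraoperative: "All drugs used intraoperatively, including total hydromorphone dose, will be collected from the electronic medical record". For the inpatient stay it says "The amount of narcotics and non-narcotic analgesics administered in the operative and postoperative period will be collected from the electronic chart", from the day of surgery until discharge. Risk and Benefits item 2 places analgesic care under the acute pain service, and Placebo Arm item 3 adds "Subjects in both arms will receive the same standard of care treatment for post-operative pain management". Neither names a postoperative opioid, a route or a duration.

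The SAP names no outcome. It provides for mainly descriptive analysis, with a possible two-sample t test.

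**The concern.** The 72-hour outcome is narrower than the quantity in the hypothesis. Opioid given by nurses, by mouth or through a PCA containing another drug adds nothing to the score. A patient whose total use is unchanged but who leaves the PCA early therefore looks like a low opioid user.

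The time of leaving the PCA comes after randomisation and may depend on pain, sedation and nausea. The Protocol itself links ketamine to these: Study Aims item 2 cites evidence that it lessens postoperative nausea and vomiting, and Risk and Benefits item 1 lists drowsiness, confusion, nausea and vomiting among its risks. Blinding does not remove an effect that acts through the drug. Earlier switching under ketamine would exaggerate a benefit; later switching would hide or reverse one.

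The pilot is meant to inform a larger trial, so an estimate that mixes opioid use with PCA duration could carry forward.

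**Working it through.** The documents give no effect size, standard deviation, alpha or power, so there is no planned figure to reproduce. The check compares the sections and then illustrates the scoring.

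**Does any section secure the measure?** Outside the brief description, PCA appears only in the literature background (Study Aims item 2). The visit procedures order none, and postoperative analgesia is left to standard care. Nothing in the documents ensures that hydromorphone PCA is started, or that it runs for 72 hours.

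**Effect on one patient's score.** Inputs: the 72-hour window (Protocol); a switch time t, a constant opioid rate and an equianalgesic switch (all assumed). PCA-only total as a share of the full total = t/72, so the apparent fall = 1 − t/72.

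| Switch at t | Fall in PCA-only total | Change in all-opioid total |
|---|---|---|
| 24 h | 1 − 24/72 = 66.7% | 0% |
| 36 h | 1 − 36/72 = 50.0% | 0% |
| 48 h | 1 − 48/72 = 33.3% | 0% |
| 60 h | 1 − 60/72 = 16.7% | 0% |

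For scale, Study Aims item 2 says of earlier positive trials that "it was generally reported to give a 30-50% reduction of rescue analgesics". A fall of 50% corresponds to t = 36 h and one of 30% to t = 0.70 × 72 = 50.4 h. The cited effect is a group comparison and the table is per patient, so the match shows only that the distortion is not trivial.

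**Switching that differs by arm.** Let d be the excess share of switchers in the ketamine arm (assumed). The false difference, as a fraction of the full 72-hour total, is d × (1 − t/72):
- t = 24 h: 6.7%, 20.0% and 33.3% for d = 0.1, 0.3 and 0.5.
- t = 48 h: 3.3%, 10.0% and 16.7% for the same d.

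With 20 patients allocated 1:1 (10 per arm if balanced), d = 0.3 is three patients. A negative d reverses the sign.

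**Switching that is equal.** If all patients in both arms switch at t and rates are constant, the retained share of a true absolute difference is t/72: 33.3% at 24 h and 66.7% at 48 h. No false difference arises. The ratio of the arm means is unchanged in this special case, so the dilution is of the difference in milligrams.

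**The case against.** The strongest reply is that the remedy largely exists. Study Design item 3 already lists an all-opioid primary outcome in morphine equivalents, and the chart extraction supports it. If that entry governs, the PCA wording does no harm. This stands to the extent that the defect is confined to the brief description. It does not dispose of the point: both texts are in the approved Protocol, the SAP does not choose between them, and only the brief description has a 72-hour window.

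Second, silence about PCA does not show that patients will not receive it. That is right: standard care may well include hydromorphone PCA. Even so, nothing stated keeps it as the only opioid source for 72 hours.

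Third, the percentages are shares of time and become shares of dose only at a constant rate. Study Aims item 2 describes the first 48 hours as the period of most pain. If use is concentrated there, the loss after a 48-hour switch would be below 33%.

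Fourth, clinicians are blinded and no data on switching by arm are given, so a false arm difference is possible rather than shown. This stands.

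Fifth, a reader might take the entry criterion, "Oral morphine equivalent of 60 mg/day or higher", to mean that at least 60 × 3 = 180 mg per patient goes uncounted. The documents do not support that: no section says that the home regimen is resumed outside the PCA, and a fixed dose given equally in both arms would cancel from the absolute difference.

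**Conclusion.** The point holds for the 72-hour outcome in the brief description. Its definition does not match the hypothesis, conflicts with Study Design item 3, and counts opioid given another way as opioid avoided. Under a constant rate and an equianalgesic switch, one patient's score can fall by 67%, 50% or 33% (switch at 24, 36 or 48 hours) with no change in total use. The rate, the switch times and any difference in switching between arms are assumptions.

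Three stronger readings go too far. The trial does not lack an all-opioid outcome, because Study Design item 3 has one. The documents do not show that patients will be off hydromorphone PCA. Nor do they show a result tilted towards ketamine: bias needs switching that differs by arm, and its direction is unknown.

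For a 20-patient, mainly descriptive pilot with no decision rule tied to PCA use, this should be corrected but does not undermine the trial.

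**What to change.** Reconcile Basic Information item 3 with Study Design item 3, and name the resulting outcome in the SAP:
- Define the 72-hour opioid outcome as all opioids by any route, in oral morphine equivalents, from fascial closure to 72 hours.
- Take it from the chart data already collected under Research Activities item 1.
- State the conversion table in advance.
- State in advance the analysis rule for patients discharged before 72 hours, because chart collection ends at discharge. Report the number of such patients by arm.
- Report hydromorphone PCA as a component only.

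A further total from the study-drug bolus onward is possible, since intraoperative drugs are recorded, but it is optional. No analgesic regimen is proposed.

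The cost is an amendment to the wording, the conversion table and the early-discharge rule. Inpatient data collection and patient burden do not change.
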